7.2.2.5.3 Urinalysis

Urinalysis samples will be collected at every visit (Table 7-1). A midstream, second voided morning urine sample will be obtained. Bilirubin, blood, glucose, ketones, leukocytes esterase, nitrite, pH, protein, specific gravity, urobilinogen will be assessed. Microscopic analysis will be performed only in case of positive dipstick.

In addition, urine samples for urinary protein/creatinine ratios will be collected at every visit (Table 7-1). First morning void samples must not be used for this analysis.

For patients who develop proteinuria or a worsening of pre-existing proteinuria (assessed by a dipstick) at any visit, please refer to Section 6.3.1.4.

7.2.2.5.4 Pregnancy and assessments of fertility

All female patients capable of becoming pregnant will have a pregnancy test (serum β - human chorionic gonadotropin) at Screening Visit 1. A urine pregnancy text will be performed at Visit 3 and at EOT (Visit 28/Month 24). The results of the test must be available prior to

^{**}Microscopic urine assessment is only required if positive urine dipstick

initiating treatment with any study medication. Positive pregnancy tests will exclude a patient from participating in this trial.

Any pregnancy during the study must be recorded on a Clinical Trial Pregnancy Form and reported by the investigator to the local Novartis Clinical Safety & Epidemiology Department (see Section 8.4 for reporting a pregnancy/pregnancy related SAE) and deferasirox must be discontinued. Pregnancy follow-up must be recorded on the same form and must include an assessment of the possible relationship to the Novartis study drug of any pregnancy outcome. Any SAE experienced during pregnancy must be reported on the SAE Report Form.

7.2.2.5.5 Hepatitis test

Hepatitis test consists of the following items: Hepatitis B Surface Antibody (Anti-HBs), Hepatitis C Antibody (Anti-HCV), Hepatitis B surface Antigen (HBsAg), Qualitative w/confirmation, HCV PCR (Quantitative). Hepatitis test will be conducted at Screening Visit 1 to assess patient eligibility. A positive text will exclude patient from the study.

7.2.2.6 Radiological examinations

Chest X-ray will be performed at Screening Visit 1 (if clinically indicated). If any chest X-ray has been performed 3 months prior to study entry the last available result will be used.

7.2.2.7 Cardiac assessments

7.2.2.7.1 Electrocardiogram (ECG)

A standard 12 lead ECG will be performed

- at Screening Visit 1
- at Visit 16 and
- at Visit 28 (EOT)

Interpretation of the tracing must be made by a qualified physician and documented on the ECG eCRF page. Each ECG tracing should be labeled with the study number, patient initials (where regulations permit), patient number, date, and kept in the source documents at the study site. Clinically significant abnormalities present at Screening should be reported on the Medical History eCRF page. Clinically significant findings must be discussed with Novartis prior to enrolling the patient in the study. New or worsened clinically significant findings occurring after informed consent must be recorded on the AE eCRF page.

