8.1 Adverse events

8.1.1 Definitions and reporting

An AE is defined as the appearance of (or worsening of any pre-existing) undesirable sign(s), symptom(s), or medical condition(s) that occur after signed informed consent has been obtained from the patient/legal patient representative.

Abnormal laboratory values or test results occurring after informed consent constitute AEs only if they induce clinical signs or symptoms, are considered clinically significant, require therapy (e.g., hematologic abnormality that requires transfusion or hematological stem cell support), or require changes in study medication(s).

Except for screening failures, AEs that begin or worsen after informed consent should be recorded in the AE eCRF. Conditions that were already present at the time of informed consent should be recorded in the Relevant Medical History/Current Medical Conditions eCRF page. Adverse event monitoring should be continued for at least 30 days following the last dose of study treatment. Adverse events (including laboratory abnormalities that constitute AEs) should be described using a diagnosis whenever possible, rather than individual underlying signs and symptoms. When a clear diagnosis cannot be identified, each sign or symptom should be reported as a separate AE.

Severity of AEs will be assessed as mild, moderate, or severe. Information about any deaths (related to an AE or not) will also be collected using an EOT form.

The occurrence of AEs should be sought by non-directive questioning of the patient during the screening process after signing informed consent and at each visit during the current study. Adverse events also may be detected when they are volunteered by the patient during the screening process or between visits, or through physical examination, laboratory test, or other assessments. As far as possible, each AE should be evaluated to determine:

- 1. The severity grade (mild, moderate, or severe).
- 2. Its duration (Start and end dates or Ongoing at End of Study).
- 3. Its relationship to the study treatment (Reasonable possibility that AE is related: No, Yes).
- 4. Action taken with respect to study treatment (none, dose adjusted, temporarily interrupted, permanently discontinued, unknown, not applicable).
- 5. Whether medication or therapy was given (no concomitant medication/non-drug therapy, concomitant medication/non-drug therapy).
- 6. Whether it is serious, where a SAE is defined as in Section 8.2.1.

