10.4.1 Variable

The primary objective of this study is safety. The safety set will be used for the analysis of safety parameters.

The overall observation period in this study will be divided into 3 mutually exclusive segments:

- 1. Pre-treatment period: from day of patient's informed consent to the day before first dose of study medication
- 2. On-treatment period i.e. from day of first dose of study medication to 30 days after last dose of study medication
- 3. Follow-up period i.e. starting at day 31 after last dose of study medication

Any AEs during on-treatment period and changes from Baseline over time during on-treatment period for serum creatinine, creatinine clearance, ALT/SGPT, AST/SGOT, RBC, platelets and white blood cell will be analyzed.

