10.4.2 Statistical hypothesis, model, and method of analysis

Descriptive statistical analyses will be performed to summarize the primary endpoints and include:

- Frequencies, percentages, and 95% confidence intervals (CIs) for overall incidences of any AEs during the on-treatment period.
- Number (n), mean, standard deviation, minimum, lower quartile, median, upper quartile and maximum time to AE.
- Number (n), mean, standard deviation, minimum, lower quartile, median, upper quartile and maximum for laboratory values for selected laboratory parameters at Baseline, and after Months 6 and 12.
- Mean \pm SE plots for laboratory values for selected laboratory parameters at Baseline, and after Months 6 and 12.

For all analysis purposes Baseline refers to the Day 1 (Visit 3) of the current study.

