10.5.2.3 Other safety data

Electrocardiogram

ECG will be performed at Baseline and after 12 months. Abnormalities will be reported together with an overall interpretation of the findings. Any abnormalities at Baseline will be summarized. The investigator will flag all abnormalities which are new or worsened since Baseline. All new or worsened abnormalities will be recorded on the AE eCRF page. All findings of patients with new or worsened clinically significant abnormalities will be listed.

Vital signs

Vital signs and body weight measured more than 30 days after discontinuation of study medication will be excluded from the analysis.

The absolute change from Baseline weight will be summarized by scheduled visit with n, mean, SD, minimum, median, and maximum values.

The criteria for notably abnormal vital signs and weight are displayed in Table 10-2.

Table 10-2 Definition of notable ranges for vital signs and weight

Parameter	Criteria for notable ranges
Systolic blood pressure	≥ 180 mmHg/≤ 90 mmHg with increase/decrease from Baseline of ≥ 20 mmHg
Diastolic blood pressure	≥ 105 mmHg/≤ 50 mmHg with increase/decrease from Baseline of ≥ 15 mmHg
Pulse rate	≥ 120 bpm/≤ 50 bpm with increase/decrease from Baseline of ≥ 15 bpm
Weight	≥ 7% increase or decrease from Baseline weight

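### Protocol 10.5.2.3 sends every new or worsened ECG abnormality to the AE page, in conflict with the ECG section (7.2.2.7.1) and the AE definition (8.1.1)

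*Protocol*

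**What the plan says.** Three parts of the protocol bear on when an ECG change becomes an adverse event.

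- Section 7.2.2.7.1, the ECG procedure: "New or worsened clinically significant findings occurring after informed consent must be recorded on the AE eCRF page".
- Section 8.1.1, the general AE definition: "Abnormal laboratory values or test results occurring after informed consent constitute AEs only if they induce clinical signs or symptoms, are considered clinically significant". The sentence goes on to add results that require therapy or a change in study medication.
- Section 10.5.2.3, in the statistics chapter: "The investigator will flag all abnormalities which are new or worsened since Baseline", then "All new or worsened abnormalities will be recorded on the AE eCRF page", then "All findings of patients with new or worsened clinically significant abnormalities will be listed".

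On timing, 10.5.2.3 says "ECG will be performed at Baseline and after 12 months". Section 7.2.2.7.1 and Table 7-1 schedule ECGs at Screening Visit 1, Visit 16 (Month 12) and Visit 28 (EOT).

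AEs are part of the primary endpoint. Section 10.4.1 names as the primary variable "Any AEs during on-treatment period and changes from Baseline over time" for selected laboratory tests. Section 10.4.2 reports "Frequencies, percentages, and 95% confidence intervals (CIs) for overall incidences of any AEs during the on-treatment period".

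**The concern.** Section 10.5.2.3 has no threshold of clinical significance where the other two sections have one. An asymptomatic, clinically insignificant tracing change that needs no therapy and no study-drug change is not an AE under 8.1.1, yet 10.5.2.3 requires it on the AE page.

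Once on that page, nothing downstream removes it. The study is single-arm, so no comparator group would carry the same extra events. A reader of the AE tables could not tell which recording rule lay behind an ECG term.

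**Working it through.** The plan states no figure on this point, so the check is a comparison of texts followed by tracing where the data go.

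**Step 1. Apply each section to the possible kinds of new or worsened on-treatment ECG change.**

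| Kind of change | 7.2.2.7.1 | 8.1.1 | 10.5.2.3 |
|---|---|---|---|
| Clinically significant | AE page | AE | AE page |
| Not clinically significant, but symptomatic or requiring therapy or a study-drug change | Not addressed | AE | AE page |
| None of these | Not addressed | Not an AE | AE page |

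The sections collide in the last row. The restriction comes from 8.1.1. Section 7.2.2.7.1 says what must be recorded and does not itself exclude anything.

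**Step 2. Is the wider wording shorthand?** No. Within one paragraph, 10.5.2.3 uses the wide class for flagging and for AE recording, and the narrow, clinically significant class for the listing.

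**Step 3. Is it settled elsewhere?** No.

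- SAP Section 2.6.1 defines a treatment-emergent AE by onset date or increase in severity and has no rule on ECG findings.
- SAP Section 2.9.4.1 plans ECG listings and does not say which findings become AEs.
- SAP Section 4 covers only the removed subgroups and baseline serum ferritin.
- The Amendment 1 log names changes to several parts of Section 10 but not to 10.5.2.3.

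**Step 4. Where would the extra events appear?** The post-baseline ECGs are at Visit 16 and Visit 28, two per patient. With the SAP's planned maximum of 58 patients, that is at most 58 × 2 = 116 scheduled tracings. The EOT visit of a patient who stops early falls within 7 days of the last dose, inside the on-treatment period, which runs to 30 days after it. A recorded change would therefore enter:

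- incidence overall and by severity, with Clopper-Pearson intervals (SAP 2.6.2);
- the tables by system organ class and preferred term (SAP 2.9.1);
- exposure-adjusted incidence by preferred term (SAP 2.9.1).

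**Step 5. How far could overall any-AE incidence move?** Let p be the proportion of patients with some other treatment-emergent AE. Let q be the proportion of the remaining patients whose only event is an insignificant ECG change. Incidence then rises from p to p + (1 − p)q, because a patient already counted is not counted again.

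The documents give neither p nor q. Purely as an illustration, assume p = 0.80 and q from 0.10 to 0.30:

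- q = 0.10: 0.80 + 0.20 × 0.10 = 0.82
- q = 0.30: 0.80 + 0.20 × 0.30 = 0.86

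That is 2 to 6 percentage points. The Clopper-Pearson interval for 46 of 58 (79%) is about 67% to 89%, so both values lie inside it. A smaller p leaves more room for movement. Counts for an ECG term have no such cushion, but without a rate they cannot be projected.

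**The case against.** The strongest reply is that the protocol already shows which rule is meant. Section 8.1.1 is the AE definition and 7.2.2.7.1 agrees with it. The physical-examination section (7.2.2.1) and the auditory and ocular section (7.2.2.4) also use a threshold of significance. The baseline ECG variable is recorded as clinically significant abnormality, yes or no. Section 10.5.2.3 stands alone, in a chapter that sites would not normally use as a recording instruction. The study is descriptive and tests no hypothesis.

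Much of this stands, and it limits what may be concluded. Four stronger readings are tempting, and the documents do not support them.

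- *Two rules of equal standing decide the primary endpoint.* They do not have equal standing: 10.5.2.3 is the outlier against the AE definition and the ECG section.
- *Sites recorded ECG changes differently.* Nothing shows that any site used Section 10 for recording.
- *The primary AE result is materially distorted, by an amount that can be calculated.* No rate of insignificant ECG changes is given, and any percentage would be the reader's own assumption.
- *The EOT ECGs are lost because 10.5.2.3 names only 12 months.* SAP Section 2.9.4.1 lists all ECG data, so the timing mismatch loses nothing and does not change the AE count.

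The reply does not remove the contradiction. Section 10.5.2.3 addresses the investigator directly on flagging, and the AE-page sentence follows at once. Its wording is current and it is wrong against 8.1.1.

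**Conclusion.** The point holds as an error of wording with a limited consequence. The AE-recording sentence in 10.5.2.3 contradicts 8.1.1 and does not match 7.2.2.7.1. If followed, it would bring tracing changes that are not AEs into the treatment-emergent AE data.

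The size is unknown. The effect would show mainly in the ECG preferred-term, mild-severity and exposure-adjusted tables. The expectation that overall any-AE incidence would move little rests on most patients having another AE during up to 24 months of treatment plus 30 days, which is plausible but not stated in the documents. Confidence is high on the textual conflict and low on any particular magnitude. The difference in ECG timing is a minor, separate wording matter.

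**What to change.** In Protocol 10.5.2.3, limit the AE-recording sentence to new or worsened abnormalities that are clinically significant or that otherwise meet the AE definition in Section 8.1.1. The second limb is needed because 8.1.1 also admits results that are symptomatic or that require therapy or a study-drug change. All other changes stay on the ECG eCRF page and in the SAP's listing of all ECG data. They would not belong in the listing of new or worsened findings, which both documents restrict to clinically significant abnormalities.

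In the same paragraph, give the post-baseline ECG times as Visit 16 (Month 12) and Visit 28 (EOT), to match 7.2.2.7.1 and Table 7-1.

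The cost is two phrases in a protocol amendment or a site clarification. No new data and no new analysis are required.

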7.2.2.7.2 Cardiac imaging - MUGA (multiple gated acquisition) scan or echocardiogram

Not applicable.

7.2.2.7.3 Cardiac enzymes

Not applicable.

7.2.2.8 Tolerability

Not applicable.

7.2.3 Pharmacokinetics

Not applicable.

7.2.4 Biomarkers

Not applicable.

Other assessments

Not applicable.

7.2.5 Resource utilization

Not applicable.

7.2.6 Patient reported outcomes

Not applicable.

8 Safety monitoring and reporting

8.1 Adverse events

8.1.1 Definitions and reporting

An AE is defined as the appearance of (or worsening of any pre-existing) undesirable sign(s), symptom(s), or medical condition(s) that occur after signed informed consent has been obtained from the patient/legal patient representative.

Abnormal laboratory values or test results occurring after informed consent constitute AEs only if they induce clinical signs or symptoms, are considered clinically significant, require therapy (e.g., hematologic abnormality that requires transfusion or hematological stem cell support), or require changes in study medication(s).

Except for screening failures, AEs that begin or worsen after informed consent should be recorded in the AE eCRF. Conditions that were already present at the time of informed consent should be recorded in the Relevant Medical History/Current Medical Conditions eCRF page. Adverse event monitoring should be continued for at least 30 days following the last dose of study treatment. Adverse events (including laboratory abnormalities that constitute AEs) should be described using a diagnosis whenever possible, rather than individual underlying signs and symptoms. When a clear diagnosis cannot be identified, each sign or symptom should be reported as a separate AE.

Severity of AEs will be assessed as mild, moderate, or severe. Information about any deaths (related to an AE or not) will also be collected using an EOT form.

The occurrence of AEs should be sought by non-directive questioning of the patient during the screening process after signing informed consent and at each visit during the current study. Adverse events also may be detected when they are volunteered by the patient during the screening process or between visits, or through physical examination, laboratory test, or other assessments. As far as possible, each AE should be evaluated to determine:

- 1. The severity grade (mild, moderate, or severe).
- 2. Its duration (Start and end dates or Ongoing at End of Study).
- 3. Its relationship to the study treatment (Reasonable possibility that AE is related: No, Yes).
- 4. Action taken with respect to study treatment (none, dose adjusted, temporarily interrupted, permanently discontinued, unknown, not applicable).
- 5. Whether medication or therapy was given (no concomitant medication/non-drug therapy, concomitant medication/non-drug therapy).
- 6. Whether it is serious, where a SAE is defined as in Section 8.2.1.

All AE's should be treated appropriately. If a concomitant medication or non-drug therapy is given, this action should be recorded on the AE eCRF.

Once an AE is detected, it should be followed until its resolution or until it is judged to be permanent, and assessment should be made at each visit (or more frequently, if necessary) of any changes in severity, the suspected relationship to the study treatment, the interventions required to treat it, and the outcome.

8.1.2 Laboratory test abnormalities

8.1.2.1 Definitions and reporting

Laboratory abnormalities that constitute an AE in their own right (are considered clinically significant, induce clinical signs or symptoms, require concomitant therapy or require changes in study treatment), should be recorded on the AE eCRF. Whenever possible, a diagnosis, rather than a symptom should be provided (e.g. anemia instead of low hemoglobin). Laboratory abnormalities that meet the criteria for AEs should be followed until they have returned to normal or an adequate explanation of the abnormality is found. When an abnormal laboratory or test result corresponds to a sign/symptom of an already reported AE, it is not necessary to separately record the lab/test result as an additional event.

Laboratory abnormalities, that do not meet the definition of an AE, should not be reported as AEs. A severe event does not automatically indicate a SAE unless it meets the definition of serious as defined below and/or as per investigator's discretion. A dose hold or medication for the laboratory abnormality may be required by the protocol in which case the laboratory abnormality would still, by definition, be an AE and must be reported as such.

8.1.3 Adverse events of special interest

Adverse events of special interest are defined as events (serious or non-serious) which are ones of scientific and medical concern specific to the sponsor's product or program, for which ongoing monitoring and rapid communication by the investigator to the sponsor may be appropriate. Such events may require further investigation in order to characterize and understand them.

Protocol No. CICL670AIC04

Adverse events of special interest are defined on the basis of an ongoing review of the safety data. Adverse events of special interest are discussed in detail in the IB.

8.2 Serious adverse events

8.2.1 Definitions

Serious adverse event (SAE) is defined as one of the following:

- Is fatal or life-threatening
- Results in persistent or significant disability/incapacity
- Constitutes a congenital anomaly/birth defect
- Is medically significant, i.e., defined as an event that jeopardizes the patient or may require medical or surgical intervention to prevent one of the outcomes listed above
- Requires inpatient hospitalization or prolongation of existing hospitalization,
- Note that hospitalizations for the following reasons should not be reported as serious adverse events:
 - Routine treatment or monitoring of the studied indication, not associated with any deterioration in condition
 - Elective or pre-planned treatment for a pre-existing condition that is unrelated to the indication under study and has not worsened since signing the informed consent
 - Social reasons and respite care in the absence of any deterioration in the patient's general condition
- Note that treatment on an emergency outpatient basis that does not result in hospital admission and involves an event not fulfilling any of the definitions of a SAE given above is not a serious adverse event

8.2.2 Reporting

To ensure patient safety, every SAE, regardless of suspected causality, occurring after the patient has provided informed consent and until at least 30 days after the patient has stopped study treatment must be reported to Novartis within 24 hours of learning of its occurrence.

Any SAEs experienced after this 30 days period should only be reported to Novartis if the investigator suspects a causal relationship to the study treatment. Recurrent episodes, complications, or progression of the initial SAE must be reported as follow-up to the original episode within 24 hours of the investigator receiving the follow-up information. An SAE occurring at a different time interval or otherwise considered completely unrelated to a previously reported one should be reported separately as a new event.

Information about all SAEs is collected and recorded on the Serious Adverse Event Report Form; all applicable sections of the form must be completed in order to provide a clinically thorough report. The investigator must assess and record the relationship of each SAE to each specific study treatment (if there is more than one study treatment), complete the SAE Report Form in English, and submit the completed form within 24 hours to Novartis. Detailed instructions regarding the SAE submission process and requirements for signatures are to be found in the investigator folder provided to each site.

Page 51

Follow-up information is submitted in the same way as the original SAE Report. Each re-occurrence, complication, or progression of the original event should be reported as a follow-up to that event regardless of when it occurs. The follow-up information should describe whether the event has resolved or continues, if and how it was treated and whether the patient continued or withdrew from study participation.

If the SAE is not previously documented in the IB or Package Insert (new occurrence) and is thought to be related to the Novartis study treatment, an oncology Novartis Chief Medical Office and Patient Safety (CMO&PS) department associate may urgently require further information from the investigator for Health Authority reporting. Novartis may need to issue an Investigator Notification, to inform all investigators involved in any study with the same drug that this SAE has been reported. Suspected Unexpected Serious Adverse Reactions (SUSARs) will be collected and reported to the competent authorities and relevant ethics committees in accordance with Directive 2001/20/EC or as per national regulatory requirements in participating countries.

